7.0 Study Procedures

The sub-study consists of two NIRF lymphatic imaging sessions (see Section below for NIRF procedure) separated by approximately two (2) weeks. At each session, measurements of the subject's head and neck will be recorded and 3D images and/or digital photographs will be taken before and after treatment. Participants will don the head and neck and vest garments before undergoing Treatment Program H1 with the Flexitouch System. Imaging with NIRFLI system will

occur before, during and after treatment with the Flexitouch System. The first NIRF lymphatic imaging session will establish the presence of lymphatic dysfunction as visualized with the NIRFLI System. The subject will be loaned the Flexitouch® Advanced Pneumatic Compression system along with the Head Garment and Vest for Head & Neck. The subjects will be instructed in the proper fitting of the garments and the use of the Flexitouch system. The subjects will complete the Flexitouch Treatment Program H1 (~30-40 minutes or ~60 minutes) daily for approximately two (2) weeks. Participants will be asked to keep a diary of their daily use on the Flexitouch System. After approximately two (2) weeks of daily use, the subject will return for the second and final NIRF lymphatic imaging session, at which time they will return the Flexitouch System and associated garments to the research team. Subjects will then be asked a series of questions related to the ease of use of the Flexitouch System and their perception of the treatment they received while using the Flexitouch System.

NIRF Lymphatic Imaging

[REDACTED]

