1.0 General Information

There were nearly 62,000 new head and neck cancer (HNC) cases last year accounting for 3% of all cancers in the US (1) with an increasing incidence among younger adults due to the human papillomavirus (HPV) infection. Treatment is typically surgical resection of primary lesions and extensive lymph node (LN) dissection, followed by fractionated radiation therapy (RT). Because the neck and cervical region contains 1/3 of the body’s LNs (2) surgical disruption of the lymphatic vasculature and LNs together with subsequent RT of the head and neck region results in the debilitating condition of lymphedema and extensive fibrosis in an estimated 75% of all HNC survivors (3, 4). Although the cure rate of these patients is high with extensive LN dissection and RT, the debilitating effects of this treatment significantly reduces the quality of survivorship. HNC lymphedema can have a profound effect on the range of motion, swallowing, and evening breathing.

Unlike breast cancer where a 10% increase in arm volume is used for diagnosis of lymphedema, there is no accepted objective measurement to base the diagnosis of HNC lymphedema. Weight loss and extensive surgery can mask the early signs of edema and lymphedema. As a result, HNC patients/survivors are not screened for lymphedema and early treatment of manual lymphatic drainage to move accumulated tissue fluid and prevent irreversible tissue changes is typically not offered to HNC cancer survivors.

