3.0 Objectives

The primary objective of the pilot study is to use NIRF imaging to assess whether pneumatic compression can move lymph in HN cancer patients and survivors. The secondary objectives are to assess whether compliant use over a two week period can reverse or reduce the dermal backflow that is associated with HN lymphedema and to collect patient feedback on the ease of use and perception of symptom alleviation with the Flexitouch System and associated head and neck garments after two weeks of daily home use.

The Flexitouch System and associated garments for extremities and trunk are approved for use by patients who are under medical supervision for the treatment of 1) lymphedema (primary or secondary); 2) edema resulting from mastectomies, trauma, sports injuries or post immobilization; 3) venous insufficiencies; 4) wounds and 5) stasis dermatitis, venous stasis ulcers, arterial leg ulcers and diabetic leg ulcers. The variety of garments and accessories available with the Flexitouch system are designed to provide targeted compression therapy to different areas of the body. Tactile Medical™ secured FDA clearance via the 510(k) program to market their newly designed head and vest garments and Flexitouch Treatment Program H1 (Appendix A, p14). When the head garment and vest garment are used together, the resulting compression directs fluid from the head to the axilla in one continuous motion, presumably moving fluid from the head and neck region into the axilla for uptake into the regional lymphatic.

We will assess whether the Flexitouch System can move lymph from the region by using NIRF imaging before and after treatment with the Flexitouch system, as well as, after 2 weeks of compliant home use. We will assess whether Flexitouch usage is associated with alleviation of lymphedema symptoms.

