4.0 Study Design

A non-randomized, non-blinded, single site pilot study designed to assess whether NIRF imaging can report on the efficacy of the Flexitouch System used to move lymph in HNC survivors. Specifically, we will assess whether the Flexitouch System can move lymph from the region by using NIRF imaging before and after treatment with the Flexitouch system, as well as, after 2 weeks of compliant home use. Participation will require approximately 24 hours over 2 weeks. Enrollment is targeted to be completed within 3 months.

Assessment of efficacy and safety

[REDACTED]

[REDACTED]

The Flexitouch System, when used for upper and lower extremity lymphedema is a standard-of-care PCD treatment device used routinely in the clinic and for at-home use. In this study, we seek to deploy NIRF imaging to assess the efficacy of the Flexitouch system for moving lymph in HNC survivors and to assess whether this correlates with symptom alleviation. [REDACTED]

[REDACTED]

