5.0 Study Population

5.1 Inclusion Criteria

- 1) Participants must be 18 years of age or older
- 2) Participants must be diagnosed with Lymphedema of the Head and/or Neck
- 3) Participants must be diagnosed with squamous cell carcinoma of the oral cavity, oropharynx or larynx and underwent surgery and/or radiation as part of their standard-of-care treatment plan.
- 4) Participants must be ≥ 4 weeks post-radiation therapy
- 5) Female participants of childbearing potential must have a negative urine pregnancy test ≤ 36 hours prior to study drug administration
- 6) Female participants of childbearing potential must agree to use a medically accepted method of contraception for a period of one month after each imaging session
- 7) Participants must be willing to use the Flexitouch[®] System at home daily for two (2) weeks

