6.0 Sample Size/Data Analysis/Subject Withdrawal and Replacement

In this pilot sub-study of a total of ten patients who complete both study visits, we will assess whether there are any changes to lymphatic function after a single use of the pneumatic compression device and after a two week period of daily home use. Five patients will undergo daily ICD of approximately 32 minutes while another five patients will undergo daily ICD of approximately 60 minutes in order to assess the effect of duration on response to therapy. If, after the initial consent and imaging session are completed, a subject withdraws, opts not to complete the daily home therapy (<75% of total treatments), OR does not properly use the device as instructed, they may be dropped from the study cohort and a replacement subject may be enrolled to ensure a full cohort of 10 subjects completes the study.

[REDACTED]

Because this is a pilot study, we cannot statistically power the study for conclusions. Instead we will assess results to visualize trends for a subsequent properly powered study to statistically test the hypothesis that the Flexitouch system can restore lymphatic function.

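### On the visible text, symptoms are asked about at most once, after two weeks of non-blinded use, so the two broader symptom aims have no measured starting point; confirm a baseline, add one, or narrow the wording

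*Combined protocol and SAP*

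**What the plan says.** The symptom aims appear in three forms.

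- Section 3.0 gives the formal secondary objective: to "collect patient feedback on the ease of use and perception of symptom alleviation with the Flexitouch System", after two weeks of home use.
- The same section later says: "We will assess whether Flexitouch usage is associated with alleviation of lymphedema symptoms".
- Section 4.0 wants imaging to show whether the device moves lymph, and "to assess whether this correlates with symptom alleviation".

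Section 4.0 describes the design as "A non-randomized, non-blinded, single site pilot study".

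Section 7.0 sets out the visits. Both sessions include head and neck measurements, photographs or 3D images, and near-infrared imaging. The first mention of questions comes when the subject is back for the final session and returns the device: "Subjects will then be asked a series of questions related to the ease of use of the Flexitouch System and their perception of the treatment". The diary in Section 7.0 records daily use, and Section 12.4 gives its purpose as compliance.

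**The concern.** Alleviation is a change from a starting state. If that state is not recorded, the subject must recall it about two weeks later, knowing the treatment received. The resulting rating combines current symptoms, memory of earlier ones and expectation, and the data give no way to separate them.

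The two broader statements would then pair unlike quantities: a measured change on the imaging side and a recalled change on the symptom side. Such a rating can still be set beside imaging change, but less securely than a measured one. The loss cannot be repaired later, because pre-treatment symptoms can no longer be measured once the first treatment has begun. It matters for a pilot whose stated purpose is to inform a later, powered study: paired symptom values are something that study could use.

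**Working it through.** The documents give no alpha, power, effect size or standard deviation for this aim, and no figure for recall error. The check is therefore a count of assessment points in Section 7.0 and a comparison of passages.

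**Step 1. Visible assessment points per subject**

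| Quantity | Derivation | Total | Recorded at session 1? |
|---|---|---|---|
| Near-infrared imaging | 3 phases (before, during, after treatment) × 2 sessions | 6 | Yes |
| Photographs or 3D images | 2 (before, after treatment) × 2 sessions | 4 | Yes |
| Head and neck measurements | at least 1 × 2 sessions | at least 2 | Yes |
| Questions to subjects | final session only | 1 | No |
| Symptom questions before first use | none visible | 0 | No |

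**Step 2. Does the one set of questions cover symptoms?** The Section 7.0 sentence names ease of use and perception of the treatment. It does not name symptoms. That symptoms are covered is inferred from the secondary objective in Section 3.0. The supported count is therefore at most 1 symptom assessment, not exactly 1.

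**Step 3. Does anything else visible supply a starting value?**

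- The diary covers use and compliance; no symptom entries are mentioned.
- Section 5.1 requires only a diagnosis: "Participants must be diagnosed with Lymphedema of the Head and/or Neck". It sets no symptom level.
- Section 1.0 says "there is no accepted objective measurement to base the diagnosis of HNC lymphedema". This concerns diagnosis rather than symptom rating, so it adds little beyond showing that enrolment does not standardise severity.
- The measurements and imaging at session 1 document physical state and lymphatic dysfunction. They are real baseline data, but not symptom ratings.
- No symptom questionnaire is named, and the only listed attachment (Section 16.0) is the device user's guide.

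**Step 4. Consequence for a symptom change**

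Paired change = symptom rating at session 2 − symptom rating at session 1.

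- Visible schedule: the session 1 term is absent, so 0 of 10 completers have a paired change.
- Same questions asked at both sessions: 2 symptom points per completer, so up to 10 of 10 have one.

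**Step 5. Each aim against the data**

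| Aim | Needs | Visible data |
|---|---|---|
| Collect perceived symptom relief (3.0) | A rating after two weeks | Sufficient |
| Use associated with alleviation (3.0) | A symptom change | Recalled change only |
| Lymph movement correlates with alleviation (4.0) | Imaging change and symptom change | Imaging change measured (Section 9.0 specifies dermal backflow area); symptom change recalled |

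**The case against.** The strongest reply is that the redactions fall where the answer would be. In Section 4.0 the heading on assessing efficacy and safety is followed only by redacted blocks, and the correlation sentence is followed by more. Sections 6.0, 7.0 and 9.0 also lose text, and the material between Sections 13.0 and 15.0 is not available. A reader might infer that the protocol leaves out a baseline symptom measure. The documents do not support that, because one may sit in the unseen text. This part of the objection stands in full, and it is why confirmation comes first.

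Second, the formal objective asks only for perception, and Section 7.0 collects perception. The two broader sentences could be shorthand for the same thing. This also stands in part: a reader might infer that the secondary objective cannot be met, and that is wrong. But as written, the two sentences speak of association and correlation with alleviation, not of perceived alleviation. If shorthand was meant, a wording change settles the matter.

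Third, a baseline would change little: the study is small, disclaims statistical conclusions, is non-blinded and describes no untreated comparator in the visible text. It is true that a paired change could not be attributed to the device and that expectation bias would remain. What the baseline removes is reliance on memory of the starting state, and it does so at visits already planned.

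**Conclusion.** The point holds in a limited form and is one to consider. On the visible text, subjects are asked about symptoms at most once, after about two weeks of non-blinded use. That satisfies the narrow secondary objective. It leaves the association and correlation aims resting on recalled change, without the measured starting point that imaging and head and neck measurements have.

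The size is 0 visible paired symptom changes among 10 completers, against up to 10 of 10 if a baseline is added. The amount of recall bias cannot be derived from the documents. The conclusion assumes that the redacted and unavailable text contains no baseline symptom measure; if it does, the point reduces to listing that measure in the visit narrative. The primary objective and the dermal backflow objective do not depend on symptoms and are untouched.

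**What to change.** 1. Confirm whether a baseline symptom measure already exists in the text not visible here. If it does, list it in the Section 7.0 visit narrative.
2. If it does not, add to Section 7.0 the same short set of symptom questions before the first treatment at session 1 and before treatment at session 2. Both ratings are then taken before that day's treatment. Keep the existing ease-of-use and perception questions at the final session.
3. Report each subject's paired symptom change descriptively, beside that subject's two-week change in dermal backflow area. Label any correlation exploratory.
4. If only a retrospective rating is intended, narrow the broader statements in Sections 3.0 and 4.0 to perceived alleviation. No data collection then changes.

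The cost is a few minutes of subject time at each of two existing visits and one case report form page, or a wording edit alone. Sample size and visits stay the same. A difference score carries measurement error from both time points, and the expectation bias and lack of an untreated control noted above remain.

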8.0 Data and Safety Monitoring

The Principal Investigator will be responsible for the monitoring of study data and subject safety. Due to the small number of research subjects, the most comprehensive and effective method of monitoring will be an individual case review by the PI ([name]) and clinical investigators ([name]; [name]; and physician designates). As this has always been the policy of the PI, the researchers and study team are under specific instructions to make the PI aware of all adverse events, expected or unexpected; therefore, the responsibility for reporting adverse events is shared with the PI and the research team.

Case Report Forms (CRFs) containing all monitoring information will be completed by the PI, clinical investigator(s) or designee and reviewed by the PI and clinical investigator(s). Case report forms (CRFs) will be kept in a locked office or archive.

[REDACTED]

[REDACTED]

9.0 Statistics

In this pilot sub-study we will assess whether there are any changes to lymphatic function after a single use of the pneumatic compression device and after a two week period of compliant use.

[REDACTED]

[REDACTED] Specifically, we seek to determine the change in the percentage of area that is demarked by dermal backflow in response to the Flexitouch System use after a single session and after two weeks of compliant use.

[REDACTED]

Because this is a pilot study, we cannot statistically power the study for conclusions. Instead we will assess results to visualize trends for a subsequent properly powered study to statistically test the hypothesis that the Flexitouch system can reduce dermal backflow and restore lymphatic function.

10.0 Ethics

This sub-study will be submitted to the local IRB, the Committee for the Protection of Human Subjects (CPHS), for approval to begin research and study oversight.

Informed consent will be conducted by a member of the research team. When possible, a copy of the consent will be provided to the study candidate prior to the clinic visit. At the first clinic visit, a private room will be used to review the consent with the candidate and to answer any questions or concerns they may have regarding participation in the research study.

11.0 Data handling and record keeping

Physical records related to the study are kept in a secure location, with controlled access. Electronic records are maintained on a secure server, behind a firewall, with restricted access by username and password. A study specific identifying will be assigned to each participants in lieu of personal identifiers.

12.0 Quality control and assurance

This study will be conducted in accordance with Good Clinical Practice (GCP) and International Conference on Harmonization (ICH) Guidelines, Code of Federal Regulations (CFR), state and local guidelines and institutional research policies and procedures to ensure subject safety and quality of data.

Raw data will be collected on the appropriate source document worksheets. Data collected in the source will be transcribed by the research staff onto paper Case Report Forms (CRFs).

12.1 Product Release Information

Product release information for ICG will be maintained by the manufacturer.

12.2 Accountability of Test Products

Indocyanine Green (ICG)

A record of lot number and expiration date will be maintained for ICG used in this study.

Near-infrared fluorescence lymphatic imaging (NIRFLI)

Flexitouch® Advanced Pneumatic Compression System

Site personnel must maintain a device accountability log. Completion of this log will ensure that all Flexitouch® Advance Pneumatic Compression pumps and garments are properly tracked and accounted for throughout the study, from the time they are received by the research team to the time they are returned to Tactile Medical. Device location, subject ID assigned, date and final disposition (e.g. return to Tactile Medical, garment discarded, etc.) of all control units and garments will be documented.

12.3 Protocol Modifications / Deviations

Protocol amendments will be submitted to the UTHSC-H CPHS (IRB) for approval prior to implementation. Protocol deviations will be acknowledged according to UTHSC-H CPHS policies, including electronic notification through the iRIS system at UTHSC-H. Exceptions to the protocol will be approved by the UTHSC-H CPHS prior to implementation.

12.4 Subject Compliance

Flexitouch® Advanced Pneumatic Compression System

Subject compliance will be evaluated through a daily diary completed by each subject.

13.0 Publication Plan

All information obtained in this study may be used for publications, presentations and conferences of a medical or scientific nature. All patient identifiers will be removed before data is disseminated in presentations and publications and any image will be de-identified to the greatest extent possible.

16.0 Attachments

Appendix A: Flexitouch User's Guide
